- **Study Design:** A randomized, double-blind, placebo-controlled, parallel-group study of flexible dose mixed salts amphetamine (5-60 mg) adjunctive to antidepressant therapy among adult outpatients with major depressive disorder responding inadequately to current antidepressant therapy.

Fig. 1: Treatment Groups

Visit	Phase	Weeks	Group	Group	Procedures
		on med	1	2	
V1		Scr			Inclusion/Exclusion
V2		0			Baseline measurement + disp.
V3	Ι	1	MSA	PBO	Measure effect of 1 week on study med + disp.
V4	Ι	2	MSA	PBO	Measure effect of 2 weeks on study med + disp.
V5	Ι	3	MSA	PBO	Measure effect of 3 weeks on study med + disp.
V6	II	4	MSA	MSA	Measure effect of 3 weeks on study med + disp.
V7	II	5	MSA	MSA	Measure effect of 3 weeks on study med + disp.
V8	II	6	MSA	MSA	Measure effect of 3 weeks on study med
V9		(8)			Safety follow-up

Fig. 2: Study Design Overview

The treatment phase of the study consists of 2 phases (21 treatment days per phase). Study Phase 1 will consist of visits 2 (baseline) through 5. Study Phase 2 will consist of visits 6 through 8. There will be a follow-up visit 2 weeks following visit 8. There is a one-week interval between study visits, with a scheduling window of \pm 3 days allowed.

Mixed salts amphetamine is FDA-approved for Attention Deficit-Hyperactivity Disorder (ADHD) and superior in efficacy to placebo; therefore, comorbid ADHD will be statistically controlled as a continuously-variable covariate, but will not be considered an exclusionary condition.

The primary analysis will be a repeated measures analysis of variance using a mixed-effects model (PROC MIXED-MMRM). The primary outcome measure will be the MGH-CPFQ total score at baseline and the MGH-CPFQ total score at the end of the trial. The independent variables will be the study visit, the treatment in the previous phase, and treatment assignment. The variance covariance matrix for the repeated measures will be unspecified.

Enrollment Period: The enrollment period is estimated to be 6 months. The last patient is expected to complete the study by March 31, 2010.

Number of Subjects: 40 subjects will be randomized (20 to each treatment arm). Additional subjects may be consented to allow for screen failures. Subjects who terminate early post-randomization will be replaced only sufficiently to ensure a total number of 24 (12 to each treatment arm) evaluable subjects.

Duration of Subjects' Study Participation: There will be a total of 9 study visits over a period of 9 weeks.

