Study Assessments and Primary Endpoints: The difference in absolute change in score from baseline to endpoint in the MGH-CPFQ between the MSA and the PBO groups is the primary endpoint. Key secondary endpoints will be difference in absolute change from baseline in MADRS score between MSA and PBO, difference in remission rates (MADRS < 11) between MSA and PBO, the change from baseline in total score at endpoint of MGH-CPFQ item analysis, difference in change scores on the CGI-S, CGI-I and QIDS. Safety outcome measures: adverse events, physical examinations, vital signs; blood pressure, orthostatic; EKG; Rush Sexual Inventory (RSI).

Statistical Methods: The randomized sample includes all patients who are randomized. The Safety sample will include those randomized patients who received at least one dose of doubleblind study medication as indicated on the dosing record. The efficacy sample will include those patients in the safety sample who have at least one efficacy evaluation post-randomization. The last observation carried forward (LOCF) data set includes data recorded at a given visit after randomization, or, if no observation is recorded at that visit, data carried forward from the previous postrandomization visit. The LOCF data set is primary, and analysis of the observed case data set also will be conducted.

The primary analysis will compare pooled MGH-CPFQ response rates between PBO and MSA and PBO non-responders. Differences in response rates will be compared using the CMH General Association Test. Descriptive statistics on non-primary groups will be conducted.

This study seeks to estimate the strength of any statistically significant relationship, or effect size, in addition to statistical significance of found treatment effects.

Secondary Endpoints Analysis: Differences in remission (defined as an endpoint MADRS score <11) rates will be compared using the CMH General Association Test. Logistic regression analysis will be performed to explore the relationship between response and patients' demographics and prognostic variables including baseline QIDS score, gender, site, and age, etc. Similar analyses will be performed for remission.

Fig. 3	: Stud	y Proce	dures	Table
--------	--------	---------	-------	-------

			Treatment period 1			Treatment period 2			
Study Visit	V1 Screen	V2 Baseline	V3	V4	V5	V6	V7	V8	V9 F/UP
End of Week	-1	0	1	2	3	4	5	6	8
Day	-7	0	7	14	21	28	35	42	56
Informed consent	Х								
Demographic data	Х								

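### The plan makes the LOCF-filled data set primary alongside an MMRM, which discards the model's own handling of missing visits and can shift the MSA-placebo difference in either direction

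*Combined protocol and SAP*

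**What the plan says.** The Study Design section states: "The primary analysis will be a repeated measures analysis of variance using a mixed-effects model (PROC MIXED-MMRM)". It adds: "The variance covariance matrix for the repeated measures will be unspecified", which I read as an unstructured covariance. It places the primary outcome at baseline and at the end of the trial.

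Under Statistical Analysis, the primary endpoint is continuous: "The difference in absolute change in score from baseline to endpoint in the MGH-CPFQ between the MSA and the PBO groups is the primary endpoint". Statistical Methods then defines LOCF visit by visit: "if no observation is recorded at that visit, data carried forward from the previous postrandomization visit". It ranks the data sets: "The LOCF data set is primary, and analysis of the observed case data set also will be conducted". No model is named for the observed-case analysis, and no missing-data assumption is stated.

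The next paragraph names a different primary analysis: "The primary analysis will compare pooled MGH-CPFQ response rates between PBO and MSA and PBO non-responders", with the test given as "Differences in response rates will be compared using the CMH General Association Test".

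On loss of subjects, Number of Subjects randomizes 40 and replaces leavers "only sufficiently to ensure a total number of 24 (12 to each treatment arm) evaluable subjects". The dosing section withdraws subjects who do not tolerate study drug. Study Procedures gives early terminators the Visit 9 procedures, and the Fig. 3 table lists neither MGH-CPFQ nor MADRS at Visit 9.

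**The concern.** An MMRM fitted to observed scores uses every recorded visit. If dropout depends only on observed scores (missing at random, MAR), it needs no imputation. Once gaps are filled by LOCF, no visit is missing after a subject's first post-randomization score. With an arm-by-visit term and an unstructured covariance, the contrast at a given visit then becomes a comparison of carried-forward scores, and the stated reason for the method is lost.

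This trial is plausibly exposed in three ways:

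- Withdrawal for intolerance can differ between a stimulant and placebo.
- Dosing starts low and is titrated upward, so an early leaver is frozen at an early-titration score. Because MGH-CPFQ is not scheduled at the termination visit, the carried score is an older one.
- If the endpoint is the end of the trial, Group 2 leavers from Phase 1 carry placebo scores into visits at which Group 2 is on MSA.

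What is at stake is the headline estimate of a 40-subject trial.

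**Working it through.** **Inputs from the documents.** 20 randomized per arm; at least 12 evaluable per arm; LOCF from the previous post-randomization visit; Group 2 switches to MSA in Phase 2. The plan gives no SD, correlation, effect size, alpha or dropout rate, so it has no figure of its own to reproduce. The replacement floor allows (40 - 24)/40 = 40% of subjects not to be evaluable. That is a floor for the whole trial, not an expected rate.

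**Assumptions, none from the documents.** Scores in SD units; a negative difference favours MSA; the mean paths and dropout rates stated below.

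**Step 1: closed form, dropout unrelated to scores (MCAR).** For each arm, the LOCF endpoint mean = sum over k of P(last visit = k) × mean at visit k. With constant dropout per interval, total loss d and two intervals (V3 to V5), h = 1 - (1 - d)^(1/2).

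- d = 40%: h = 0.2254, so P(last = V3) = 0.2254 and P(last = V4) = 0.1746.
- d = 10%: h = 0.0513, so P(last = V3) = 0.0513 and P(last = V4) = 0.0487.

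If an arm improves linearly by m up to V5, a leaver last seen at V3 falls short by 2m/3 and one last seen at V4 by m/3. The arm's mean shortfall is m × w(d), with

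- w(40%) = 0.2254 × 2/3 + 0.1746 × 1/3 = 0.2085
- w(10%) = 0.0513 × 2/3 + 0.0487 × 1/3 = 0.0504

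Bias = MSA shortfall - placebo shortfall:

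| Mean improvement at V5 (MSA / PBO) | Loss (MSA / PBO) | Bias |
|---|---|---|
| 0.5 / 0.5, linear | 40% / 10% | 0.5 × (0.2085 - 0.0504) = +0.079 |
| 0.8 / 0.3, linear | 40% / 40% | (0.8 - 0.3) × 0.2085 = +0.104 |
| 0.8 / 0.3, linear | 40% / 10% | 0.8 × 0.2085 - 0.3 × 0.0504 = +0.152 |
| 0.8 / 0.3, linear | 10% / 40% | 0.8 × 0.0504 - 0.3 × 0.2085 = -0.022 |
| 0.8 / 0.3, reached by V3 then flat | 40% / 10% | no shortfall: 0.000 |

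Unequal loss is therefore neither sufficient for bias (last row) nor necessary (second row), and the sign can change.

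**Step 2: dropout depending on the last observed score (MAR), by simulation, 20 per arm.**

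- No true difference, both arms improving 0.3/0.6/0.9 SD at V3/V4/V5, placebo loss 11%. LOCF bias at V5 is 0.06, 0.11 and 0.16 SD for MSA loss of 21%, 29% and 37%. It is -0.16 SD when placebo has the larger loss. The MMRM on observed scores, at 11% against 37%, has bias 0.01 SD.
- A separate set-up (correlation 0.6, both arms improving linearly to 0.5 SD, 40% MSA and 10% placebo loss): LOCF bias +0.147, observed-data MMRM +0.002.
- Same set-up with a true difference of -0.50 (linear 0.8 against 0.3, 40% / 10%): LOCF averages -0.271 and the MMRM -0.505.
- Flat after V3, 40% / 10%: LOCF averages -0.434 against a true -0.50, a bias of about +0.07. The zero in the last row of the table therefore holds only under MCAR.

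**Step 3: carry-over across phases, contrast at V8 (MCAR, five intervals).** MSA improves to 0.8 by week 3 and stays there. Group 2 improves to 0.3 by week 3 and, after the switch, to 0.8 by week 6. The true V8 difference is 0. With 40% loss in both arms, h = 1 - 0.6^(1/5) = 0.0971. The shortfall is 0.075 for MSA and 0.195 for Group 2, so the bias is 0.075 - 0.195 = -0.120. With 10% MSA and 40% Group 2 loss it is -0.178. Both favour the arm on MSA throughout.

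**Step 4: precision.** In two simulations under differential MAR dropout, the mean model standard error of the LOCF contrast was 0.304 and 0.306, against empirical SDs of 0.304-0.309 and 0.303. It is not understated. Sampling SD is about 0.30 for LOCF and 0.34 for the MMRM in the first set-up of Step 2, a ratio of 0.34/0.30 = 1.13.

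**The case against.** **The link is inferred.** No sentence says that the MMRM uses LOCF rows, and the primary analysis named in Statistical Methods is a CMH test, which has no likelihood handling of missing data. This stands, and the competing statements must be reconciled. It does not rescue LOCF, since a CMH test on the filled set would classify leavers by a carried score.

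**The size rests on assumptions.** This stands too. The dropout splits and mean paths are assumed, and the 40% is a replacement floor.

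**Mean squared error need not improve.** At 11% against 37% loss, LOCF gives √(0.30² + 0.16²) = 0.34 and the MMRM √(0.34² + 0.01²) = 0.34. So the gain is removal of bias, not lower total error. When MSA loses more subjects in Phase 1, the bias runs against MSA: one rerun found false rejections favouring MSA at about 0.5% against a nominal 2.5%. The cost there is power. The direction reverses if placebo loses more or, in the scenario of Step 3, if placebo scores are carried into Phase 2 with equal loss.

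**Some mitigation is planned.** An observed-case analysis would expose sensitivity to LOCF, but its model is not stated and it is not primary.

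**Stronger readings to avoid.** A reader might infer that the difference is biased whenever the arms lose subjects at different rates; the flat-mean case in Step 1 contradicts this. A reader might also infer that copied scores make the standard error too small. Each subject contributes one score to the contrast at a visit, and Step 4 shows agreement between model and empirical values. Nor do simulated false-positive rates of 7.7% (LOCF) and 6.2% (MMRM) carry weight: with 1,200 trials, each has a simulation error of 0.7-0.8 points.

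**Conclusion.** The point holds as a risk of bias, not a certainty. Read together, the two sections put the primary MMRM on filled data and so forgo its handling of missing visits. The bias can go either way. It depends on how means change after dropout, when dropout occurs, and how dropout relates to outcome. Under assumed losses of roughly 10% on placebo and 20-40% on MSA, with both arms improving, it is about 0.06-0.16 SD at V5, against about 0.01 SD for the MMRM on observed scores. If the contrast is at V8, placebo scores carried into MSA visits can create a difference of about -0.12 SD with equal 40% loss and no true difference. The near-zero MMRM bias holds under MAR with an arm-by-visit mean model and unstructured covariance. The documents do not establish that dropout will differ by arm, or by how much.

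**What to change.** Before unblinding, amend the plan as follows:

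1. State that the primary analysis of MGH-CPFQ change is the MMRM fitted to observed scores without imputation, and that it is valid under MAR. Exchanging the rank of the two data sets is not enough, because the observed-case model is not named.
2. Name the visit of the primary contrast, and make sure the model contains the term needed to estimate it.
3. Keep LOCF as a sensitivity analysis only.
4. Reconcile this with the sentence that makes a CMH test of response rates primary. For any CMH analysis of response or remission, pre-specify a rule other than LOCF, such as counting a missing score at the analysis visit as not responded or not remitted. That rule is also a single imputation and should be labelled as a convention.

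The cost is a few sentences, plus settling which analysis and time point are primary. The confidence interval would be modestly wider, by about 13% in the assumed scenario (sampling SD 0.34 against 0.30).

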- 1. Primary outcome: The group treated with MSA adjunctive to ADT will show a greater mean change from baseline to endpoint in total score as compared to the group treated with placebo (PBO) adjunctive to ADT as measured by the
 - a. Massachusetts General Hospital Cognitive-Physical Function Questionnaire (MGH-CPFQ)
- 2. Secondary outcome:
 - a. MSA adjunctive to ADT will demonstrate clinically acceptable safety and tolerability, compared to placebo, based on
 - i. spontaneously reported adverse events and significant adverse events
 - ii. significant changes in blood pressure and pulse
 - iii. significant changes in weight
 - iv. significant changes in electrocardiogram
 - v. significant changes in the Rush Sexual Inventory
 - b. The group treated with MSA adjunctive to ADT will show a greater mean change from baseline to endpoint as compared to the group treated with PBO adjunctive to ADT as measured by the change on
 - i. MGH-CPFQ individual item analysis
 - ii. MADRS scores:
 - 1. Total score
 - 2. Subscales
 - 3. Individual item analysis
 - 4. Percent of "responders" (\geq 50% reduction in score baseline to endpoint)
 - 5. Percent reaching "remission" (score of ≤ 10 at endpoint)

- c. The group treated with MSA adjunctive to ADT will show statistically significant improvement in core residual symptoms of MDD extant on monotherapy ADT as measured by the
 - i. PGI (Patient Impression and Improvement) scales
 - ii. Quick Inventory of Depressive Symptomatology-16 (QIDS-16) total score (≤ 6) and subscale
 - iii. Clinical Global Impression-Severity (CGI-S); and, Clinical Global Impression-Improvement (CGI-I)
 - iv. QIDS total score and subscale
- d. The group treated with MSA adjunctive to ADT will show statistically significantly improvement in overall functioning (work, social and cognitive) when compared to the group treated with PBO and ADT as measured by the
 - i. Total and individual item scores from the HDRS-17 and -28
 - ii. Maier and other subscale scores from the HDRS-17 and -28
 - iii. Scale For Assessment Of Negative Symptoms (SANS)
 - iv. Health Status Questionnaire, 2nd ed. (HSQ 2.0)
 - v. SF-36 Health Survey (SF36)
 - vi. Fawcett Experienced Pleasure Index (EPI)
 - vii. Endicott Work Productivity Scale (EWPS)
 - viii. Sheehan Disability Scale (SDS)
 - ix. Fatigue Associated with Symptoms of Depression (FASD)

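### Two different analyses are each named as primary, nothing ranks them, and neither names a visit at which one arm is still on placebo

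*Combined protocol and SAP*

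**What the plan says.** **Hypothesis.** Under Research Hypotheses, the primary outcome is that the MSA group "will show a greater mean change from baseline to endpoint in total score as compared to the group treated with placebo", measured by the MGH-CPFQ. The Primary Endpoints paragraph of Statistical Analysis agrees: the endpoint is the MSA-placebo difference in absolute change in score. Neither text dates the endpoint.

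**First primary analysis.** Study Design states: "The primary analysis will be a repeated measures analysis of variance using a mixed-effects model (PROC MIXED-MMRM"). It continues: "The primary outcome measure will be the MGH-CPFQ total score at baseline and the MGH-CPFQ total score at the end of the trial", and "The independent variables will be the study visit, the treatment in the previous phase, and treatment assignment".

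**Second primary analysis.** Statistical Methods states: "The primary analysis will compare pooled MGH-CPFQ response rates between PBO and MSA and PBO non-responders". The rates are to be compared by the CMH general association test. The same section makes the LOCF data set primary, with observed cases also analysed.

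**Treatment by phase.** In Study Design and Study Procedures, Group 1 takes MSA in both phases. Group 2 takes placebo in Phase 1 (Visits 2 to 5) and MSA in Phase 2 (Visits 6 to 8). Phase 2 drug is handed out at Visit 5, so Visit 5 is the last assessment with a placebo arm.

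**The concern.** The two analyses differ in outcome scale, method and comparison groups. With both called primary and neither ranked, the choice between them can be made after the results are known. The CMH version also does not estimate the quantity that the hypothesis and the endpoint paragraph describe.

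The time point is a second problem. The trial's only randomised comparison of MSA with placebo lies in Phase 1, yet the one time point that is stated is the close of the trial, when everyone is assigned MSA. A comparison of the arms there asks whether six weeks of MSA differ from three, which is not the stated hypothesis.

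**Working it through.** **1. The two statements side by side**

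| | Study Design | Statistical Methods |
|---|---|---|
| Outcome | MGH-CPFQ total, continuous | MGH-CPFQ response, binary |
| Method | MMRM | CMH general association |
| Groups | Treatment assignment, plus prior-phase treatment | PBO, MSA and PBO non-responders, pooled in an unstated way |
| Time point | Close of the trial | None |
| Fits the continuous endpoint | Yes | No |

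**2. Can the CMH test be run as written?** No. The plan's only responder rule, "50% reduction in score baseline to endpoint", is listed under MADRS. No MGH-CPFQ cut-off, visit or strata are given. PBO non-responders are not defined, and no re-randomisation of them is described: all of Group 2 moves to MSA.

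**3. Does the model's prior-phase term fix the contrast?** Phase 1 has no previous phase, so the result depends on a coding that the plan does not give.
- *Left missing in Phase 1.* Those rows drop out. On Visits 6 to 8 the design has five columns (intercept, two visit terms, prior-phase treatment, treatment). Prior-phase treatment equals the randomised arm, and current treatment is constant. The rank is 4 of 5 under either meaning of assignment, so the treatment term cannot be estimated.
- *Coded as none in Phase 1.* The treatment term can be estimated. Assume no visit-by-treatment term and an effect of 1/3, 2/3 and 1 over the first three weeks on MSA. Under compound symmetry the term is (1/3 + 2/3 + 1)/3 = 0.667 of the Visit 5 effect, which is the mean Phase 1 difference. Under AR(1) with correlation 0.5, 0.7 or 0.9 it is 0.583, 0.521 or 0.417. An immediate effect is recovered in full.

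**4. LOCF.** A missing visit takes the value from the previous post-randomisation visit, with no limit by phase. A Group 2 subject who leaves during Phase 1 would therefore contribute a placebo score to Visits 6 to 8. The plan does not say whether the MMRM uses this data set.

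**5. Size of the time-point problem.** The plan states no alpha, power, effect size or SD, so its sample size of 40 cannot be reproduced. The inputs below are assumed: two-sided alpha 0.05, standardised difference d = 0.8 at Visit 5, and a fraction f of it left at week 6. The two-sample t test has noncentrality f × d × √(n/2). The sizes are the planned 20 per arm and the floor set "to ensure a total number of 24 (12 to each treatment arm) evaluable subjects".

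| Visit, f | n = 20: noncentrality, power | n = 12: noncentrality, power |
|---|---|---|
| Visit 5, f = 1 | 2.530, 0.693 | 1.960, 0.466 |
| Week 6, f = 0.5 | 1.265, 0.234 | 0.980, 0.155 |
| Week 6, f = 0.25 | 0.632, 0.095 | 0.490, 0.076 |
| Week 6, f = 0 | 0, 0.050 | 0, 0.050 |

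**6. Size of the free choice.** In a null simulation of 40,000 runs, a t test stood in for the continuous model and a CMH test used an assumed 30% response rate. Taking whichever was significant at one time point gave a type I error of 8.3% (20 per arm) or 8.1% (12 per arm). With week 3 or week 6 also open, and visit correlation 0.5 to 0.7, it was about 13% to 15%.

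**The case against.** **The phases are not ignored.** The endpoint is worded as MSA against placebo, and placebo exists only in Phase 1. The Study Design model also carries a prior-phase term. A reader might infer that the plan has no link to Phase 1 at all. The documents do not support that: step 3 shows a coding under which the treatment term, with compound symmetry, rests on Phase 1 alone. What stands is narrower. The link is implied and never stated, it depends on an unstated coding, and the one time point given points away from Phase 1.

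**The list of model terms may not be complete.** It names independent variables and does not rule out interactions. The fair criticism is that no contrast or visit is named, not that a visit-specific effect is impossible.

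**The pooled test may do no harm.** A reader might infer that it adds Phase 2 MSA outcomes of placebo non-responders to the MSA side and so produces false successes. That is one guess at an ambiguous sentence, and its result turns on assumptions. With 20 per arm, an assumed 50% rule and 25% mean improvement at week 3, and Group 1 counted at Visit 5, false success ran from 0.006 to 0.067 as the assumed later drift grew. Rejection against MSA ran from 0.073 down to 0.009. Measuring Phase 2 response from Visit 5 instead cut false success to 0.002 to 0.015. No direction of bias can be claimed.

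**The study is small and partly aimed at estimation.** This is true, since the plan states an interest in effect size. But an estimate also needs one defined contrast at one time.

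**Conclusion.** Wrong as written, and to be corrected before any results are seen. The finding rests on the text alone: two unranked primary analyses, one of which does not fit the endpoint and cannot be run as specified; a stated time point at which both arms are assigned MSA; and a carry-forward rule that can move placebo scores into the MSA phase.

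The figures only illustrate the scale. Under the assumptions in step 5, moving the contrast from Visit 5 to week 6 leaves between about a third of the power (0.234 of 0.693) and none beyond the alpha level at 20 per arm. How much of a Phase 1 difference would survive Group 2's switch to MSA is unknown. The type I error figures rest on an assumed response rate and a simplified model.

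**What to change.** 1. Name one primary analysis: the Study Design mixed model of change from baseline in MGH-CPFQ total, fitted to Visits 3 to 5, with visit, randomised arm and visit-by-arm. Baseline MGH-CPFQ can be added at no cost, because it is already collected.
2. Make the primary contrast Group 1 versus Group 2 at Visit 5. Replace the end-of-trial wording in Study Design with Visit 5, and drop the prior-phase term from this model.
3. Remove the pooled response-rate CMH test as primary. Any MGH-CPFQ responder analysis is secondary, at Visit 5, between randomised arms, with a cut-off set in advance.
4. Carry no LOCF value across the Visit 5 phase boundary, and state which data set the primary model uses. Whether LOCF or observed data should come first is a separate decision.
5. Report Group 2's Phase 2 data descriptively.

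This fix should not depend on the Study Design promise that "comorbid ADHD will be statistically controlled as a continuously-variable covariate". The study procedures table lists no ADHD measure, so that covariate has no scheduled source.

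**Cost.** These are text edits in Study Design and Statistical Analysis. The end-of-trial contrast and the pooled responder test lose primary status. No visits or subjects are added, because the MGH-CPFQ is already scheduled at Visits 2 to 5.

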- 11) Pregnant or breastfeeding women.

Study Procedures: Figure 3 shows study procedures to be performed at each visit. No study procedures will be performed until a subject signs the informed consent document.

Screen visit (Visit 1): Medical and psychiatric history will be taken, a physical examination and vital signs will be performed and lab tests done. Lab tests include CBC, CMP, urine drug screen and urine pregnancy test for females of childbearing potential. If a subject has had the required lab tests performed within the past 3 months and can produce the results, lab procedures may be waived at the screening visit for that patient (except urine pregnancy test). The HDRS-17 score upon screening will be used to determine entry eligibility (see inclusion criteria). Beyond the patient's verbal report, we will attempt to obtain medical records (e.g., previous clinician or pharmacy records) to document adequate dose and duration of previous/current ADT.

Study Phase 1

Baseline visit (Visit 2): Screened and eligible subjects will return one week after the screening visit. At this visit (provided entry criteria continue to be met) subjects will be randomized in double-blind fashion to one of two treatment groups:

- Group 1: MSA during both phases; or
- Group 2: PBO during Phase 1 followed by MSA during phase 2

Study drug will be dispensed to the subject in sufficient quantity to last until the next study visit (7 days +/-3).

Study visits 3-5: Following the baseline visit, subjects will return at one-week intervals for study visits 3-5. Study procedures to be performed are reflected in Figure 3. Phase 2 study drug is dispensed at study visit 5.

Study visits 6-8: Subjects will return at one-week intervals for study visits 6-8. Study procedures to be performed are reflected in Figure 3. At visit 8, all subjects will receive instructions for tapering the dose of the MSA to avoid potential difficulties from abrupt discontinuation of the study drug.

Study visit 9: Subjects will return two weeks following visit 8 for a safety follow-up check. Procedures to be performed are reflected in Figure 3.

If a subject withdraws or is terminated early from the study, visit 9 procedures will be performed at the final study visit.

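### The pooled primary response analysis brings in placebo non-responders whose Phase 2 data have no placebo control, so that component is either empty or biased

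*Combined protocol and SAP*

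**What the plan says.** Under Statistical Analysis, the Statistical Methods text states: "The primary analysis will compare pooled MGH-CPFQ response rates between PBO and MSA and PBO non-responders". It continues: "Differences in response rates will be compared using the CMH General Association Test". It names no phase, visit, strata or weights. Response on the MGH-CPFQ is not defined anywhere; the 50% reduction rule in the Research Hypotheses belongs to the MADRS. Groups outside the primary comparison get descriptive statistics only, so placebo non-responders are meant to be part of the inferential test.

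On allocation, the Baseline visit (Visit 2) text says that "subjects will be randomized in double-blind fashion to one of two treatment groups". The two groups are "Group 1: MSA during both phases" and "Group 2: PBO during Phase 1 followed by MSA during phase 2". Fig. 3 marks randomisation at V2 only, and Fig. 1 shows MSA in both groups at V6 to V8. No step selects or re-randomises placebo non-responders.

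The Number of Subjects text plans 20 randomised per arm, with early terminations replaced only as far as needed for "a total number of 24 (12 to each treatment arm) evaluable subjects". It gives no alpha, power or assumed response rate.

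Two other statements compete with this one. Study Design names an MMRM on MGH-CPFQ total score, from baseline to the close of the trial, as the primary analysis. Study Assessments and Primary Endpoints makes the primary endpoint a difference in change score, which is continuous.

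**The concern.** Hypothesis 1 is a claim about MSA against placebo. Evidence for it can come only from a period in which randomised subjects are on one or the other, and in this design that is Phase 1, V2 to V5. Response among placebo non-responders in Phase 2 combines any drug effect with three more weeks on the background antidepressant, regression to the mean after selection on a poor V5 result, and expectancy on a patient-completed scale. Nothing in the design separates these.

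If that response is pooled into the MSA side, the result is no longer an MSA-versus-placebo effect. It could show a difference for an inert drug, or hide a real one. Because the sentence supports several readings that can give different answers, choosing among them after unblinding could change the trial's conclusion.

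**Working it through.** The plan gives no power calculation, so there is no sample-size figure to reproduce. The 20 per arm, the single randomisation and the Phase 2 treatments come from the documents. Response rates, correlations, the expectancy shift and two-sided 0.05 are assumptions.

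**1. Readings side by side**

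- Stratified by phase: the Phase 2 stratum of placebo non-responders contains only MSA.
- Unstratified: MSA side = Group 1 in Phase 1 plus placebo non-responders in Phase 2; comparator = Group 2 in Phase 1.
- Placebo non-responders against Group 1 within Phase 2: MSA against MSA.

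None has a placebo arm for the Phase 2 component.

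**2. The CMH statistic in an example**

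Take Phase 1 response of 10/20 on MSA and 6/20 on placebo, which leaves 14 placebo non-responders, and let 5 of the 14 respond on MSA in Phase 2.

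- Phase 1 alone: expected MSA responders 20 × 16/40 = 8; variance 20 × 20 × 16 × 24/(40² × 39) = 2.46; chi-square (10 − 8)²/2.46 = 1.625.
- Phase 2 added as a stratum: expected 14 × 5/14 = 5, so observed minus expected is 0. The variance has the placebo row total, 0, as a factor, so it is 0. Chi-square stays at 1.625.
- Unstratified: 15/34 against 6/20. Expected 34 × 21/54 = 13.22; variance 34 × 20 × 21 × 33/(54² × 53) = 3.05; chi-square 1.78²/3.05 = 1.04. There are 54 records from 40 people, and the 14 non-responders appear on both sides.

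**3. Bias of unstratified pooling with no drug effect**

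Let p be Phase 1 response in both arms and q the Phase 2 response of placebo non-responders for reasons other than MSA. Non-responders make up about w = (1 − p)/(2 − p) of the MSA-side records, so the apparent difference is about w(q − p). At p = 30%, w = 0.7/1.7 = 0.41; at p = 20%, w = 0.8/1.8 = 0.44. Rejection rates are from 200,000 simulated trials per row, 20 per arm.

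| p | q | Apparent MSA − PBO (points) | Rejection |
|---|---|---|---|
| 30% | 0% | −12 | 15% |
| 30% | 10% | −8 | 8% |
| 30% | 30% | 0 | 5% |
| 30% | 50% | +8 | 10% |
| 30% | 60% | +12 | 16% |
| 20% | 60% | +18 | 30% |

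Phase 1 alone rejects in about 5% in every row. The sign follows q − p. Subjects selected for not responding tend to respond less often later than an unselected group, which pushes against MSA. Continued improvement over time and expectancy push the other way.

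**4. Linking q to p**

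In the table p and q vary freely. A latent-normal model for response at V5 and V8 ties them together: V5 response 20-30%, V8 response 20-45% and not below V5, V5-V8 correlation 0.5-0.7, Phase 2 expectancy shift 0 or 0.3 SD, no drug effect, 20 per arm.

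- Group 1 scored at V5: about −6 to +14 points, rejection about 5-20%.
- Group 1 scored at V8 against placebo at V5: about −6 to +34 points, rejection about 5-74%.
- Randomised Phase 1 contrast: 0 points, about 5%.

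**5. Share of the pool**

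At 20-40% placebo response, non-responders supply about 37-44% of MSA-side records. As a share of all records, (1 − p)/(3 − p) runs from 0.6/2.6 = 23% to 0.8/2.8 = 29%.

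**The case against.** The strongest reply is that the sentence is too vague to convict. It gives no visit, strata or weights, and a phase-stratified CMH test would carry no bias because Phase 2 would drop out. That is correct, and it means the size of the bias depends on the reading. It does not rescue the text, because under that reading naming placebo non-responders has no effect. The largest figures also require scoring Group 1 at V8 against placebo at V5, which the plan does not state; they show what the wording would allow.

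A second reply is that this is part of a larger conflict, since Study Design names an MMRM and the stated endpoint is continuous. That also stands, and settling on one primary analysis might remove the sentence altogether. The MMRM does not cure the problem as written, because its final time point falls when both groups are on MSA.

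Third, this is a 40-subject study that seeks effect sizes as well as significance, and its Phase 1 comparison is sound. That limits the damage, but the text still calls the pooled test primary.

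A reader might infer that half of the primary comparison is uncontrolled. The documents give no weights, and the record shares above are below half; what holds is that one of the two components is uncontrolled. A reader might also infer a sequential-parallel enrichment design that lost its second randomisation. The plan never uses that label, and the point does not depend on it.

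**Conclusion.** The point holds. The design facts are settled by the text, Fig. 1 and Fig. 3, and under no reading do placebo non-responders have a Phase 2 placebo control. As written, the pooled primary test is either unchanged by their Phase 2 data or biased by it.

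The numerical ranges rest on the assumed response rates, correlation and expectancy shift, since the plan supplies none of these. What patients were told about Phase 2 cannot be seen, so the expectancy component in particular is an assumption.

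Two stronger conclusions are not supported. A reader might infer that the error favours MSA. With stable background response and no expectancy shift it runs against MSA, by about 3 to 6 points in the latent-normal model. A reader might also infer that the trial cannot test MSA against placebo. It can, because the randomised V2 to V5 comparison is intact and unbiased.

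**What to change.** In Statistical Methods, delete *pooled* and *and PBO non-responders*, and state that any MSA-versus-placebo response test compares the two randomised groups at V5, the end of Phase 1, on change from V2. The visit must be named: deleting the words alone would still allow a test at V8, when both groups are on MSA.

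Report Group 2's V5 to V8 course on MSA, overall and in V5 non-responders, as an uncontrolled descriptive result with no efficacy p-value.

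In the same edit, define MGH-CPFQ response and name one primary analysis, reconciling this sentence with the continuous endpoint and with the MMRM in Study Design, including its time point.

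The cost is wording only, with no added visits or patients. Phase 2 data no longer feed the primary test, but they never supplied placebo-controlled evidence. The sponsor should see what Phase 1 alone can detect. At an assumed two-sided 0.05 and 80% power, the detectable standardised difference in change score is (1.96 + 0.84) × √(2/n), which is 0.89 at 20 per arm and 1.14 at 12 per arm.
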